3.4.2. Inclusion Criteria

Subjects are required to meet the following inclusion criteria:

1.	The investigator must assess the capacity of the subject to provide informed consent during the screening period and throughout the course of the trial. Once this determination is made by the investigator, the options for obtaining informed consent from and/or on behalf of the subject must be followed as provided in Section 3.4.1 .
2.	Male and female subjects between 55 and 90 years of age, inclusive, at the time of informed consent.
3.	Subjects with a diagnosis of probable Alzheimer's disease according to the NINCDS-ADRDA criteria.
4.	Subjects with a MMSE score of 5 to 22, inclusive, at the screening and baseline visits.
5.	Subjects must have a previous MRI or CT scan of the brain, which was performed after the onset of the symptoms of dementia, with findings consistent with a diagnosis of Alzheimer's disease.
6.	Subjects who are residing at their current location for at least 14 days before screening and are expected to remain at the same location for the duration of the trial.
7.	Institutionalized subjects with an identified caregiver who has sufficient contact to describe the subject's symptoms and has direct observation of the subject's behavior. The identified caregiver can be a staff member of the institutionalized setting or another individual (eg, family member, family friend, hired professional caregiver) who meets the caregiver requirements. Non-institutionalized subjects may not be living alone (see Section 3.3.1.1 for caretaker definition) and must have an identified caregiver who has sufficient contact to describe the subject's symptoms and has direct observation of the subject's behavior.
8.	Subjects with a total score (frequency × severity) of ≥ 4 on the agitation/aggression item of the NPI-NH (for institutionalized subjects) or the NPI/NPI-NH (for non-institutionalized subjects) at the screening and baseline visits.
9.	Subjects with onset of symptoms of agitation at least 2 weeks prior to the screening visit.
10.	Subjects who require pharmacotherapy for the treatment of agitation per the investigator's judgment, after an evaluation for reversible factors (eg, pain, infection, polypharmacy) and a trial of nonpharmacological interventions.
11.	Subjects who are capable of self-locomotion or locomotion with an assistive device (eg, 4-point walker, wheelchair).
12.	Subjects willing and able to discontinue all prohibited concomitant medications to meet protocol-required washouts prior to and during the trial period.
13.	Subjects able to satisfactorily comply with the protocol requirements.

CT = computed tomography; MRI = magnetic resonance imaging; MMSE = Mini-Mental State Examination; NINCDS-ADRDA = National Institute of Neurological and Communicative Disorders and Stroke and the Alzheimer's Disease and Related Disorders Association; NPI-NH = Neuropsychiatric Inventory-Nursing Home; NPI/NPI-NH = Neuropsychiatric Assessment for Non-Institutionalized Patients based on the NPI/NPI-NH.

Protocol 331-12-283

3.4.3. Exclusion Criteria

Subjects will be excluded if they meet any of the following exclusion criteria prior to randomization:

Table 3.4.3-1 Exclusion Criteria	
Target Disease	
1.	Subjects with dementia or other memory impairment not due to Alzheimer's disease, such as mixed or vascular dementia, dementia with Lewy bodies, Parkinson's disease dementia, frontotemporal dementia, substance-induced dementia, HIV-dementia, traumatic brain injury, normal pressure hydrocephalus, or any other specific non-Alzheimer's-type dementia; subjects with a diagnosis of Down syndrome.
2.	Subjects with a previous MRI or CT scan of the brain, which was performed after the onset of the symptoms of dementia, with findings consistent with a clinically significant central nervous system disease other than Alzheimer's disease, such as vascular changes (eg, cortical stroke, multiple infarcts), space-occupying lesion (eg, tumor), or other major structural brain disease.
3.	Subjects with a history of stroke, well-documented transient ischemic attack, or pulmonary or cerebral embolism.
4.	Subjects who have an insufficient response, based on the investigator's judgment, to 2 or more previous antipsychotic medications for the treatment of agitation associated with Alzheimer's disease.
5.	Subjects with delirium or history of delirium within the 30 days prior to the screening visit.
6.	Subjects who have been diagnosed with an Axis I disorder (DSM-IV-TR criteria) including, but not limited to: 
 • Schizophrenia, schizoaffective disorder, or other psychotic disorder not related to dementia • Bipolar I or II disorder, bipolar disorder not otherwise specified • Current major depressive episode. Subjects with major depressive disorder are eligible provided that they have been on a stable dose(s) of antidepressant medication(s) for the 30 days prior to randomization. Please note: antidepressant medications that are CYP2D6 or CYP3A4 inhibitors are prohibited (see Table 4.1-2 for prohibited antidepressant medications).
7.	Subjects with evidence of serious risk of suicide based on the Sheehan Suicidality Tracking Scale (Sheehan-STS), ie, a score of 3 or 4 on any one question 2 through 6 or 11 or a score of 2 or higher on any one questions 1a, 7 through 10, or 12, or who, in the opinion of the investigator, present a serious risk of suicide.
Medical History and Concurrent Diseases	
8.	Subjects who currently have clinically significant neurological, hepatic, renal, metabolic, hematological, immunological, cardiovascular, pulmonary, gastrointestinal, or psychiatric disorders. Clinically significant cardiovascular disorders include uncontrolled atrial fibrillation, heart failure, or ischemic heart disease. Surrogates for uncontrolled cardiovascular disease would include recent (within the last 6 months) hospitalizations or procedures, such as percutaneous coronary intervention, coronary bypass surgery. 
Medical conditions that are minor or well-controlled may be considered acceptable if the condition does not expose the subject to an undue risk of a significant adverse event or interfere with assessments of safety or efficacy during the course of the trial. The medical monitor should be contacted in any instance where the investigator is uncertain regarding the stability of a subject's medical condition(s) and the potential impact of the condition(s) on trial participation.

Protocol 331-12-283

Table 3.4.3-1 Exclusion Criteria	
9.	Subjects with uncontrolled hypertension (DBP > 95 mmHg) or symptomatic hypotension, or orthostatic hypotension, which is defined as a decrease of ≥ 30 mmHg in SBP and/or a decrease of ≥ 20 mmHg in DBP within 3 minutes of standing compared to the previous supine blood pressure, OR development of symptoms. Abnormal vital signs results should be repeated to ensure reproducibility of the abnormality before excluding a subject based on the criteria noted above.
10.	
Subjects with diabetes mellitus may be eligible for the trial if their condition is stable and well-controlled as determined by satisfying ALL of the following criteria:
 
 HbA_{1c} < 8.0%, AND Screening glucose must be ≤ 125 mg/dL (fasting) or < 200 mg/dL (non-fasting). If the non-fasting screening glucose is ≥ 200 mg/dL, subjects must be retested in a fasted state and the retest value must be ≤ 125 mg/dL, AND Subject has not had any hospitalizations within the 3 months prior to screening due to diabetes or complications related to diabetes. 
Subjects with non-IDDM (ie, any subjects not using insulin) must also satisfy the below criterion:
 
 Subject has been maintained on a stable regimen of oral antidiabetic medication(s) for at least 28 days prior to screening or diabetes has been well-controlled by diet for at least 28 days prior to screening. 
Subjects with IDDM (ie, any subjects using insulin) must also satisfy the below criterion:
 
 No current microalbuminuria; ie, urine ACR must be < 30 mg/g (calculated). 
Subjects with newly diagnosed diabetes during screening are excluded.

11.	
Subjects with hypothyroidism or hyperthyroidism (unless condition has been stabilized with medications for at least the past 90 days) and/or an abnormal result for free T₄ at screening.
 
Eligibility of subjects excluded based on an abnormal free T₄ result can be discussed with the medical monitor if, in the investigator's judgment, the subject is a suitable candidate for the trial.

12.	Subjects with epilepsy or a history of seizures, except for a single childhood febrile seizure, post traumatic, alcohol withdrawal, etc.
13.	Subjects with seropositive status for hepatitis B (ie, HBsAg positive) or hepatitis C (ie, anti-HCV positive).
14.	Subjects considered in poor general health based on the investigator's judgment. Examples include subjects who have a recent clinically significant weight loss, chronic dehydration or hypovolemia, poor fluid or nutritional intake, or a recent clinically significant infection, as per the investigator's judgment.
15.	Subjects with a BMI < 18.5 kg/m ² .
16.	Subjects who have met Diagnostic and Statistical Manual of Mental Disorders , Fourth Edition, Text Revision (DSM-IV-TR) criteria for substance abuse or dependence within the past 180 days; including alcohol and benzodiazepines, but excluding caffeine and nicotine.
Physical and Laboratory Results	
17.	Subjects with a positive drug screen for cocaine, marijuana (whether medically prescribed or not), or other illicit drugs are excluded and may not be retested or rescreened. Subjects with a positive urine drug screen resulting from use of prescription or over-the-counter (OTC) medications or products that in the investigator's documented opinion do not signal a clinical condition that would impact the safety of the subject or interpretation of the trial results may continue evaluation for the trial following consultation and approval by the medical monitor.

Protocol 331-12-283

Table 3.4.3-1 Exclusion Criteria	
18.	
Subjects with abnormal laboratory tests results, vital signs results, or ECG findings, unless, based on the investigator's judgment, the findings are not medically significant and would not impact the safety of the subject or the interpretation of the trial results. The medical monitor should be contacted to discuss individual cases, as needed. Criteria are provided in Appendix 3, Appendix 4, and Appendix 5 to assist investigators in their assessments of results that may be potentially medically significant, depending on the subject's medical history and clinical presentation.
 
In addition, subjects with the following laboratory test and ECG results at screening must be excluded from the trial:
 
 • Platelets $\leq 75,000/\text{mm}^3$ • Hemoglobin $\leq 9 \text{ g/dL}$ • Neutrophils, absolute $\leq 1000/\text{mm}^3$ • Aspartate transaminase (AST) $> 2 \times \text{ULN}$ • Alanine transaminase (ALT) $> 2 \times \text{ULN}$ • Creatine phosphokinase (CPK) $> 3 \times \text{ULN}$, unless discussed with and approved by the medical monitor • Albumin $< 3 \text{ g/dL}$ • HbA_{1c} $\geq 8\%$ • Abnormal T₄, unless discussed with and approved by the medical monitor. (Note: Free T₄ is measured only if the result for thyroid-stimulating hormone [TSH] is abnormal.) • QTcF $\geq 450 \text{ msec}$ in men and $\geq 470 \text{ msec}$ in women (see Section 3.7.4.4 for further details), unless due to ventricular pacing 
Tests with exclusionary results should be repeated (if ECG, 3 consecutive recordings) to ensure reproducibility of the abnormality before excluding a subject based on the criteria noted above.

Sex and Reproductive Status	
19.	Sexually active females of childbearing potential (see Section 5.5) and male subjects who are not practicing 2 different methods of birth control with their partner during the trial and for 30 days after the last dose of trial medication or who will not remain abstinent during the trial and for 30 days after the last dose. If employing birth control, each couple must use 2 of the following precautions: vasectomy, tubal ligation, vaginal diaphragm, intrauterine device (IUD), birth control pill, birth control implant, birth control depot injections, condom with spermicide, or sponge with spermicide.
20.	Females who are breast-feeding and/or who have a positive pregnancy test result prior to receiving trial drug in Trial 331-12-283.
Prohibited Therapies or Medications	
21.	Subjects who have a current medical condition that requires treatment with an anticoagulant.
22.	Subjects who have received bapineuzumab, solanezumab, or other immunotherapy, such as vaccines, for the treatment of Alzheimer's disease (through clinical trial or compassionate use program) in the 6 months preceding randomization.
23.	Subjects who would be likely to require prohibited concomitant therapy during the trial (see Table 4.1-1).
24.	Subjects who received brexpiprazole in any prior clinical trial or commercially available brexpiprazole (Rexulti®).
Allergies and Adverse Drug Reactions	
25.	Subjects with a history of neuroleptic malignant syndrome (NMS).
26.	Subjects with a history of true allergic response (ie, not intolerance) to more than 1 class of medications.

Protocol 331-12-283

Table 3.4.3-1 Exclusion Criteria	
Other	
27.	Subjects who participated in a clinical trial within the last 30 days.
28.	Any subject who, in the opinion of the investigator, medical monitor, or sponsor should not participate in the trial.

ACR = albumin-to-creatinine ratio; anti-HCV = hepatitis C antibodies; BMI = body mass index; CT = computed tomography; CYP2D6 = cytochrome P450 2D6 isozyme; DBP = diastolic blood pressure; DSM-IV-TR = Diagnostic and Statistical Manual of Mental Disorders, 4th edition, text revision; ECG = electrocardiogram; HbA_{1c} = glycosylated hemoglobin; HBsAg = hepatitis B surface antigen; HIV = human immunodeficiency virus; IDDM = insulin-dependent diabetes mellitus; MRI = magnetic resonance imaging; QTcF = QT interval as corrected for heart rate by Frederica's formula; SBP = systolic blood pressure; T₄ = thyroxine; ULN = upper limit of normal.

Screen failures previously excluded for a positive drug screen for cocaine, marijuana, or other illicit drugs are not eligible to be retested or rescreened. Screen failures previously excluded for a positive blood alcohol test or a positive urine drug screen due to use of prescription or over-the-counter (OTC) medications or products may be retested or rescreened once for participation in the trial with consent of the medical monitor. Screen failures excluded for any other reasons may be retested (the evaluation may be repeated within the screening period) or rescreened once at any time if the exclusion characteristic has changed. A subject may be rescreened more than once after discussion with and approval by the medical monitor. In the event that a screen failure is rescreened, a new ICF must be signed, a new screening number assigned, and all screening procedures repeated.

3.5. Outcome Variables

3.5.1. Primary Efficacy Variable

The primary efficacy variable is the change from baseline to Week 12/ET in the CMAI total score. The primary analysis will use a mixed-effect model repeated measure (MMRM) approach.

3.5.2. Key Secondary Efficacy Variable

The key secondary efficacy variable is the change from baseline to Week 12/ET in the Clinical Global Impression-Severity of Illness (CGI-S) score, as related to agitation.

Protocol 331-12-283

3.5.3. CCI [Redacted]

[Redacted]

- [Redacted]
- [Redacted]
- [Redacted]
- [Redacted]
- [Redacted]

3.5.4. CCI [Redacted]

[Redacted]

- [Redacted]
- [Redacted]
- [Redacted]
- [Redacted]
- [Redacted]
- [Redacted]

3.5.5. CCI [Redacted]

[Redacted]

- [Redacted]
- [Redacted]
- [Redacted]
- [Redacted]

Protocol 331-12-283

3.5.6. Safety Variables

Safety variables to be examined in this trial will include AEs, physical and neurological examinations, vital signs, body weight, waist circumference, clinical laboratory tests (hematology, serum chemistry, and urinalysis), ECGs, CCI [REDACTED]

Adverse events will be examined by frequency, severity, seriousness, discontinuation, and relationship to treatment. Mean change from baseline and the incidence of potentially clinically relevant abnormal values will be calculated for vital signs, body weight, routine laboratory tests (including prolactin), and ECG parameters. Mean change from baseline will be calculated for coagulation parameters (prothrombin time [PT], activated partial thromboplastin time [aPTT], and International Normalized Ratio [INR]), glycosylated hemoglobin (HbA_{1c}), cortisol, adrenocorticotrophic hormone (ACTH), thyroid-stimulating hormone (TSH), waist circumference, and BMI (derived programmatically from body weight and height measurements). A central ECG service will be used to review all ECGs to standardize interpretations for the safety analysis.

CCI [REDACTED]

By-subject listings of physical and neurological examination findings will be reviewed as a further assessment of safety.

3.5.7. Pharmacokinetic/Pharmacodynamic Variables

Plasma concentrations will be determined for brexpiprazole and its metabolite(s) and descriptive statistics will be calculated. No formal statistical comparisons are planned. Additional population or pharmacokinetic or pharmacodynamic modeling may be performed as a separate analysis by combining data from this trial with data from all other trials.

3.6. Measures to Minimize/Avoid Bias

3.6.1. Randomization

During the trial, administration of the IMP will be double-blind. In other words, neither the investigator nor the subject will have knowledge of the treatment assignment (ie, placebo or brexpiprazole). Treatment assignments will be based on a computer-generated randomization code provided by the Otsuka Pharmaceutical

Protocol 331-12-283

Development & Commercialization, Inc (OPDC) Biometrics Department. Sponsor personnel, including those involved in monitoring, data management, and data analysis, will not have access to the treatment code during the trial. Access to the treatment codes will be restricted to personnel charged with generating and maintaining randomization files, packaging trial medication, operating the IVRS/IWRS, and reporting SAEs to regulatory agencies. The randomization will be stratified by center. Subjects will be randomized to brexpiprazole 1 mg/day, brexpiprazole 2 mg/day, or placebo in a 1:1:1 ratio within each stratum.

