Three studies of another compound discovered by Otsuka, aripiprazole (Abilify[®]), have been conducted to investigate its benefit in the treatment of psychosis in subjects with Alzheimer's dementia.^{21,22,23} In the 2 of the 3 aripiprazole trials that were conducted in subjects in institutional settings such as nursing homes, benefit in the treatment of agitation in that subject population was suggested by the finding of statistically significant differences between the aripiprazole treatment groups and the placebo treatment groups on 2 secondary endpoints, the Cohen-Mansfield Agitation Inventory (CMAI) and the agitation item of the Neuropsychiatric Inventory-Nursing Home (NPI-NH). In the fixed dose trial, which included 2 mg/day, 5 mg/day, and 10 mg/day dose arms, there were significant differences found on both measures for the 5 mg/day and 10 mg/day groups. Significant differences compared with placebo on both measures were also observed in the second flexible-dose trial of the 2 mg/day to 15 mg/day dose range.

Because of concerns about tolerability and safety in subjects, the doses of antipsychotics used in clinical trials in subjects with dementia have generally been lower than the doses recommended for subjects with schizophrenia.^{21,22,24} While the dose range for brexpiprazole in schizophrenia studies is 1 mg/day to 4 mg/day, the selected dose range in the Alzheimer's population is 1 mg/day to 2 mg/day, to maximize tolerability while investigating doses that should achieve the occupancy of the D2 receptor associated with benefit in the alleviation of target symptoms by a D2 partial agonist. Slow titration of the dosing will also be employed to maximize tolerability.

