3.7.2. Efficacy Assessments

It is required that adequately trained and experienced clinicians administer the CMAI, NPI-NH, NPI/NPI-NH, CGI-S, CCI and CCI. In addition, the raters must be certified for this trial to administer the CMAI, NPI-NH, and NPI/NPI-NH. Notations in the subject's trial records should substantiate the ratings. Training, certification, and materials for rating will be provided by a rater training group.

A caregiver must be identified during the screening period for participation in the interview for the CMAI, NPI-NH, NPI/NPI-NH, and other applicable trial assessments. In addition to providing responses to trial questionnaires, the identified caregiver will be interviewed by the trial personnel regarding the subject's general medical condition, behavioral symptoms, and activities of daily living. If the subject is in an institutionalized setting, the identified caregiver will gather information from several informants, including staff from the day, afternoon, and night shifts, as well as from reliable family members or friends, in order to provide an accurate and comprehensive overview of the subject's behavioral symptoms and condition. If the subject is in a non-institutionalized setting, the identified caregiver can gather information from the caretaker (if different than the identified caregiver) or from other informants who are in a position to observe the subject and provide information regarding behavioral symptoms and activities of daily living. Details on the caregiver requirements can be found in [Section 3.3.1](#).

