7.1. Sample Size

The sample size was calculated based on the treatment effect of 6.5 points with a standard deviation (SD) of 16.5 in the change from baseline (Day 0 visit) to the end of the double-blind treatment period (Week 12 visit) in the CMAI total score, to achieve 85% power at a 2-sided alpha level of 0.05. This results in 117 subjects in each of the groups (ie, brexpiprazole 1 mg/day, brexpiprazole 2 mg/day, and placebo). After allowance of 10% non-evaluable subjects, the total number of subjects to be randomized is 132 per treatment arm. The sample size was estimated based on a 1:1:1 randomization ratio (brexpiprazole 1 mg/day, brexpiprazole 2 mg/day, placebo). CCI

Protocol 331-12-283

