7.4. Efficacy Analyses

7.4.1. Primary Efficacy Analysis

The primary endpoint will be analyzed using an MMRM model. The primary efficacy outcome measure is the mean change from baseline (Day 0 visit) to the end of the double-blind treatment period (Week 12 visit) in the CMAI total score. The primary statistical comparisons of interest are brexpiprazole 2 mg/day versus placebo and brexpiprazole 1 mg/day versus placebo. The null hypotheses of these comparisons are that there is no difference between the brexpiprazole treatment groups and placebo in change from baseline to endpoint in CMAI total score. To protect the experiment-wise 2-sided alpha level at 0.05 when making 2 comparisons of brexpiprazole doses versus placebo, the statistical testing will be carried out using a hierarchical testing procedure in the order of 1) comparison of 2 mg/day brexpiprazole versus placebo and 2) comparison of 1 mg/day brexpiprazole versus placebo. Thus, if the test yields a statistically significant result at 0.05 (2-sided) for the comparison of 2 mg/day brexpiprazole versus placebo, then the comparison of 1 mg/day brexpiprazole versus placebo will be tested at an alpha level of 0.05 (2-sided).

The statistical comparison will be performed by the MMRM analysis with an unstructured variance covariance matrix for the repeated measures in which the change from baseline (Day 0 visit) in CMAI total score (at Weeks 2, 4, 6, 8, 10, and 12) will be the dependent variable based on the OC dataset. The model will include fixed class-effect terms for treatment, trial center, visit week, and an interaction term of treatment by visit week and include the interaction term of baseline values of CMAI total score by visit week as a covariate. The primary comparison between brexpiprazole and the placebo arm at Week 12 will be estimated as the difference between least squares (LS) means from the interaction term of treatment by visit week utilizing the computing software SAS procedure PROC MIXED.

CCI

The primary analysis CCI will be performed on the Efficacy Sample.

Protocol 331-12-283

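### Care setting is neither a randomization stratum nor a term in the primary model although both settings are enrolled; the cost is some precision, not validity

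*Protocol*

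**What the plan says.** Sections 3.1 and 3.3 admit subjects living in institutions and subjects living elsewhere, provided they do not live alone. On allocation, Section 3.6.1 states: "The randomization will be stratified by center". No other stratum is named, and the ratio is 1:1:1 within each center.

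Section 7.4.1 gives the primary model: "The model will include fixed class-effect terms for treatment, trial center, visit week, and an interaction term of treatment by visit week". The same sentence adds baseline CMAI by visit week as a covariate. Care setting is not in the list. Section 7.4.2 applies the same method to the key secondary variable, the CGI-S.

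Section 3.7.2 sets the rule on informants. In an institution the caregiver "will gather information from several informants, including staff from the day, afternoon, and night shifts", and also from family or friends. Elsewhere, "the identified caregiver can gather information from the caretaker (if different than the identified caregiver") or from other people placed to observe the subject. The first rule is an instruction; the second is a permission. Section 3.3.1.1 allows the caregiver and the live-in caretaker to be different people.

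**The concern.** The protocol itself treats setting as a stable and meaningful attribute of the subject. Transfer between settings during treatment leads to withdrawal (Sections 3.3 and 3.8.3). The CMAI signal cited in Section 2.2 comes from the "2 of the 3 aripiprazole trials that were conducted in subjects in institutional settings such as nursing homes". Section 1 ties behavioral disturbance to nursing home admission. Setting is therefore a plausible predictor of CMAI change, though no figure in the protocol shows this.

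If it does predict change, leaving it out of the model keeps its variance in the residual, and the arms can differ in setting mix by chance. Center is the only control built into allocation. At about 420 subjects over about 85 sites (420/85 = 4.9 per site, under 2 per arm), it controls setting well only where a center recruits from one setting. Section 3.7 lets visits take place at the site or at a residential facility, and no text confines a center to one setting.

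The informant rule is a related matter of measurement. The CMAI rates 29 behaviors over the previous two weeks (Appendix 6). The minimum caregiver contact is 2 hours a day on 4 days a week. At home, the person who sees most of the behavior may go unasked.

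**Working it through.** **The plan's own figure.** Section 7.1 assumes a "treatment effect of 6.5 points with a standard deviation (SD) of 16.5", "to achieve 85% power at a 2-sided alpha level of 0.05". By normal approximation, n = 2 × (1.960 + 1.036)² × 16.5² / 6.5² = 115.7, so 116 per arm. The exact two-sample t calculation gives power 0.848 at 116 and 0.851 at 117, hence 117, which agrees with "This results in 117 subjects in each of the groups". The 10% allowance gives 117/0.9 = 130; the stated 132 is close and is not disputed. The standard error of a contrast at 117 per arm is 16.5 × √(2/117) = 2.16 points.

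**Inputs not in the documents.** The institutionalized share p is assumed to be 20% to 50%. The difference D between settings in mean CMAI change is assumed to be 3 to 10 points.

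**Formulas, before any center or baseline adjustment.**
- SD of the between-arm difference in setting share: √(2p(1−p)/117).
- 95% limit of the chance shift in a contrast: 1.96 × that SD × D.
- SD of change with setting in the model: √(16.5² − p(1−p)D²).
- Power: Φ(6.5 / (SD × √(2/117)) − 1.96).

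Example, p = 0.35 and D = 5: √(2 × 0.35 × 0.65/117) = 0.062; 1.96 × 0.0624 × 5 = 0.61 points; adjusted SD = √(272.25 − 5.69) = 16.33; power 0.861.

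| p | D | 95% chance shift | SD with setting | Power at 117 | n for 85% |
|---|---|---|---|---|---|
| not modeled | – | – | 16.50 | 0.854 | 116 |
| 20% | 3 | 0.31 | 16.46 | 0.856 | 116 |
| 35% | 5 | 0.61 | 16.33 | 0.861 | 114 |
| 50% | 3 | 0.38 | 16.43 | 0.857 | 115 |
| 20% | 10 | 1.03 | 16.01 | 0.874 | 109 |
| 50% | 10 | 1.28 | 15.72 | 0.885 | 106 |

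The shift runs from 0.31/6.5 = 5% to 1.28/6.5 = 20% of the planned effect. The power gain runs from 0.2 to 3.1 percentage points. These are two views of one loss and should not be added: the chance shift is already part of the unadjusted standard error.

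**How much center stratification helps.** Allocation was simulated with 420 subjects, 85 sites of unequal size and an assumed block size of 6. The 95% limit of the imbalance in setting share, for p from 20% to 50%, was:
- 9 to 12 percentage points if every center mixes the settings to the same degree;
- 7 to 9 points if centers partly specialize;
- 4 to 6 points if each center has one setting, in which case the center term in the model absorbs setting anyway.

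Unstratified allocation at 140 per arm has an SD of 4.8 to 6.0 points, or 9.4 to 11.7 points at 1.96 SD. Where centers mix settings evenly, stratifying by center therefore gives almost no protection on this factor.

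**Informant contact.** At the minimum, 2 hours × 4 days × 2 weeks = 16 hours, out of 14 × 24 = 336 hours in the CMAI recall window, or about 5%.

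**The case against.** The strongest reply is that the planned analysis is sound and already adjusts for much of this. Three parts of that reply stand.

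- Randomization protects the type I error, and the contrast is unbiased in expectation. A reader might infer that the omission biases the result; the documents do not support that.
- The baseline CMAI-by-visit covariate adjusts at each visit for initial severity, which is the link to setting that Section 1 describes. Together with the center term, it makes the figures above upper bounds. At D = 5, setting explains only 1.5% to 2.3% of the variance of change.
- The informant rule is stable within a subject and applies equally to blinded arms. The CMAI form, rater certification and recommended caregiver contact are the same in both settings.

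Two further inferences should be resisted. The different NPI versions might suggest that entry severity is measured differently. It is not: Section 3.7.2.6 says the versions differ in the disruptiveness or distress question, the entry score is frequency times severity, and the agitation anchors in Appendices 8 and 9 match. A reader might also say that the plan cannot show whether the effect holds in both settings. Results by setting may lie in the blacked-out parts of Section 7.4 or in the statistical analysis plan, so they cannot be called missing.

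It can also be said that Section 3.1 makes caretaker input optional. That sentence concerns the diary, which is not analyzed, and does not govern the CMAI interview.

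What the reply does not remove is that the strata and the model terms are stated in full and setting is in neither. Center cannot stand in for setting where a center recruits from both.

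**Conclusion.** The point holds as a matter of precision and of consistent ascertainment. Under the assumed ranges (20% to 50% institutionalized, 3 to 10 points between settings), a setting term is worth about 0.2 to 3 percentage points of power. It guards against a chance shift whose 95% limit is about 0.3 to 1.3 CMAI points before center or baseline adjustment. The true gain is smaller to the extent that centers specialize in one setting or baseline CMAI carries the same information; the documents allow neither to be sized. The upper end needs both a 10-point difference and an even split. The sample size is not in question, and the planned test is valid as it stands.

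The informant wording cannot be given a size. The protocol does not show that the CMAI is observed less completely at home, only that consulting the caretaker is left optional there.

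**What to change.** 1. In Sections 7.4.1 and 7.4.2 (and the synopsis), add care setting at baseline, institutionalized or not, as a fixed effect in the primary and key secondary models, preferably with its interaction with visit week so that the settings may follow different courses. Setting is known for every subject because it selects the NPI version. It stays fixed on treatment because transfer leads to withdrawal. Keep randomization stratified by center; crossing setting with about 85 centers would leave very sparse strata. Cost: one parameter for setting plus five for the interaction over six visits.

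2. In Section 3.7.2, where caregiver and caretaker differ, replace *can* with *will*, so that the caregiver gathers information from the caretaker before each CMAI interview, in line with the institutional rule. Cost: a short conversation before each rating.
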